## 5.2.5.3.1 Adverse Drug Reactions Requiring M6620 Treatment Discontinuation or Modifications

In the case of occurrence of an AE attributed to M6620, treatment may be interrupted and may resume when all toxicities have returned to Grade 2 or less, at the discretion of the Investigator. Except for participants in Part A during the DLT observation period, doses of M6620 may be reduced after occurrence of a related AE using the following guidelines, any exceptions to this dose modification criterion will need to be agreed between the PI and IND Office:

- a. For Grade 4 hematologic toxicity: the dose of M6620 will be reduced by 25%.
- b. For Grade 3 non-hematologic toxicity: M6620 will be discontinued.
- c. For Grade 4 non-hematologic toxicity: M6620 will be discontinued.

Guidelines for dose modification for toxicity are provided below. The final dose reduction or delay for each participant may be determined by the Investigator. However, these guidelines provide the minimum dose reduction or delay criteria. Additionally, if a participant who is responding to treatment experiences toxicity even after 2 dose reductions, the participant may continue to receive treatment if in the judgment of the Investigator it is in the best interest of the participant. In this case the dose of M6620 will further be reduced by at least 25%.

In case of M6620 Grade 3 or higher toxicity (excluding fatigue or nausea/vomiting/diarrhea adequately managed by supportive care), treatment will be interrupted and may be resumed when all toxicities have returned to Grade 2 or lower, at the discretion of the Investigator.

For the following hematologic toxicities, once the toxicity has returned to Grade 2 or lower, dosing can be resumed with 1 dose level reduction. If, after 1 dose level reduction, any of the below drug-related hematologic toxicities are subsequently observed, then dosing may be resumed with 2 dose level reductions:

- a. Grade 4 thrombocytopenia;
- Febrile neutropenia (growth factor support, per site protocol, may be used in lieu of dose reduction) except during the DLT assessment period prior to occurrence of a DLT. Once a DLT has occurred, it is acceptable to use growth factor support even during the DLT period;
- c. Grade 4 neutropenia lasting more than 7 days.

If any of the drug-related toxicity listed below is subsequently observed, the M6620 dose will be reduced by 1 dose level:

- a. Grade 3 non-hematologic toxicity (except for fatigue or nausea, vomiting, or diarrhea adequately controlled by medication). For infusion reactions, hypersensitivity, or allergic reactions related or possibly related to M6620, see below for additional guidelines for management;
- b. Any Grade 2 or lower non-hematologic toxicity requiring dose delay of more than 2 weeks.

For Grade 4 non-hematologic toxicity, treatment will be interrupted and may be resumed with 2 dose level reductions when toxicity has returned to Grade 2 or lower.

If any toxicity not described above results in a delay in dosing during any part of the study and the participant may be benefitting from therapy, then the doses of M6620 may be reduced by 1 dose level at the discretion of the Investigator.

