- 16. M6620 may be administered to patients in the dose escalation phase at 1 of 3 doses: 240 mg/m² (dose level 1), 480 mg/m² (dose level 2), or 120 mg/m² (dose level -1) IV weekly, starting on Cycle 1 Day 1 (Days 1, 8, 15, and 22 of every cycle). M6620 will be administered to patients in the dose expansion phase of at the recommended phase 2 dose (RP2D) established in the dose escalation phase.
- 17. When M6620 and Avelumab are to be administered on the same day (e.g. C1D1, C1D15), avelumab will be infused first, with an interval of at least 1 hour before infusion of M6620.
- 18. CT, MRI, or PET-CT scans will be performed at screening, and then every 2 cycles or 8 weeks (± 7 days) for the first year of treatment. Thereafter, tumor assessments will be performed every 3 cycles or 12 weeks (± 7 days) independent of cycle delays. Confirmatory scans will also be obtained ≥ 4 weeks following initial documentation of objective response (OR) or progression of disease (PD). The type of scan obtained is at the discretion of the investigator as appropriate for the disease. However, the same method should be used for the duration of the study. Baseline brain CT or MRI scan is required for all high risk patients (such as breast, melanoma and other cancer types as determined by the PI/sub I) at baseline (screening). Patients with stable brain metastases present at baseline (screening) will have brain CT or MRI scans performed at each tumor assessment. If bone metastases are present at baseline (screening), then repeat bone imaging is required every 8 weeks for the first 52 weeks of study treatment and every 24 weeks thereafter. Bone imaging is required at the time of confirmation of CR for patients who have bone metastases.
- 19. Relevant tumor markers (e.g., CA125, PSA, and CEA) will be assessed at screening, and on Day 1 of every cycle (± 7 days) this will include blood draws at EOT and Long Term Follow-up.
- 20. One tumor biopsy is mandatory (C1D15), although not mandatory all other tumor biopsies will be strongly encouraged. A core tissue biopsy may be required at baseline if no leftover tissue is available for screening, tissue is older than 1 year, or there is not enough tissue for testing. Tumor biopsies may be performed at baseline (pre-treatment), Cycle 1 Day 15, and at the time of progression/EOT (where feasible).

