Dose Level -1	M6620: 120 mg/m  , QW, IV; Avelumab: 800 mg, Q2W, IV

**Note:** other intermediate doses of M6620 may be considered following discussion with EMD Serono.

When avelumab and M6620 are to be administered on the same day, avelumab will be administered first, with an interval of at least 1 hour between infusions.

[figure not shown]

Figure 2: Dose Expansion of the combination of M6620 and avelumab (Arm A)

Interim Analysis for Safety: Patients can have any qualifying DDR aberration for interim safety analysis. We will stop if, at any time during the study, we determine that there is more than an 80% chance that the posterior probability of toxicity (i.e., DLT) is more than 30%.

2Interim Analysis for Futility: Using a 3-stage design with 10 patients in each stage, we will stop after the 1st stage if we see 0 successes in 10 patients, after the 2nd stage if we see <2 successes in 20 patients, and we will declare the treatment worthy of further study if we see >3 successes in 30 patients. If we set p0 (highest success rate for unacceptable treatment) =5% and p1 (lowest success rate for acceptable treatment) =20%, this design has alpha=5%, 80% power and probability of early termination under p0 of 60% after 1st stage and 79% after either 1st or 2nd stage.

Note: This study will not be rejected for efficacy until at least N=10 patients with ATM variants have been evaluated for efficacy.

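### Section 5.2.5.3.1 gives two M6620 reductions for Grade 4 thrombocytopenia and for Grade 4 neutropenia beyond 7 days; on the Table 1 levels, the repeat reduction has no defined dose for a patient who started at 240 mg/m²

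*Combined protocol and SAP*

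**What the plan says.** Section 5.2.5.3.1 holds two sets of instructions for reducing M6620 after toxicity.

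The first is a short list. Its hematologic item reads "For Grade 4 hematologic toxicity: the dose of M6620 will be reduced by 25" per cent. It excludes no type of Grade 4 hematologic event. The sentence introducing the list exempts participants in Part A during the DLT observation period, and sends exceptions to the PI and the IND Office for agreement.

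The second set follows. The section says that the investigator may determine the final reduction or delay, but that these guidelines are the least that must be applied. It then says "For the following hematologic toxicities, once the toxicity has returned to Grade 2 or lower, dosing can be resumed with 1 dose level reduction". If one of the listed events is seen after that reduction, "then dosing may be resumed with 2 dose level reductions". The list contains "Grade 4 thrombocytopenia", febrile neutropenia (no grade given, with growth factor allowed in place of a reduction) and "Grade 4 neutropenia lasting more than 7 days".

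The M6620 doses are defined in footnote 16 of the Study Calendar, "240 mg/m² (dose level 1), 480 mg/m² (dose level 2), or 120 mg/m² (dose level -1) IV weekly", and again in Section 3.2.1, Table 1, where the lowest row is 120 mg/m². Level 1 (240 mg/m²) is the starting level. A note under Table 1 adds that "other intermediate doses of M6620 may be considered following discussion with EMD Serono", without giving any values.

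**The concern.** The two overlapping events are hematologic and Grade 4, so each falls under both rules. A site that follows either paragraph complies with the protocol, yet the two paragraphs can lead to different doses. The term dose level is not redefined in Section 5.2.5.3.1. Read as the Table 1 levels, the repeat-event instruction can point below the lowest dose in the protocol.

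The first stake is patient safety, because this is the instruction for continuing after Grade 4 toxicity. The second is exposure. Section 5.2.5.3 bars re-escalation after a reduction for drug-related toxicity, and withdraws patients who need more than two reductions unless otherwise agreed. The size of the first step therefore carries through the rest of treatment. Section 3.5 bases the RP2D on safety and preliminary efficacy from escalation and expansion, and Section 9.6.1 describes toxicity by dose level. Both are harder to read if patients with the same event are reduced by different rules, some of them to doses that are not levels at all.

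**Working it through.** The 25% is a stated rule, not a derived figure, so there is nothing to reproduce. The check sets the two rules side by side on the protocol's own doses.

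**Inputs**
- First rule: 25% reduction (Section 5.2.5.3.1, first list).
- Second rule: one dose level, then two on a later event (Section 5.2.5.3.1, later paragraph).
- Levels: 480, 240 and 120 mg/m² (Study Calendar footnote 16; Table 1).
- Assumption: dose level in Section 5.2.5.3.1 means a Table 1 level. The protocol uses the term that way in Sections 3.2.1, 3.4 and 3.5.

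**Size of one level:** 1 − 240/480 = 50%; 1 − 120/240 = 50%. Each step is twice the 25% of the first rule.

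**First event**

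| Current dose (mg/m²) | 25% rule | One-level rule | Ratio |
|---|---|---|---|
| 480 | 0.75 × 480 = 360 | 240 | 360/240 = 1.5 |
| 240 | 0.75 × 240 = 180 | 120 | 180/120 = 1.5 |
| 120 | 0.75 × 120 = 90 | none defined | – |

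None of 360, 180 or 90 is a defined level. For the two overlapping events, a 25% cut is also smaller than the 50% step in the guidelines that the section itself calls a minimum.

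**Later event under the level rule.** The text does not say whether two levels are counted from the original dose or from the current one.
- Started at 480, reduced to 240: counted from the original dose, 120; counted from the current dose, none defined.
- Started at 240, reduced to 120: none defined on either count.
- Started at 120: the first one-level step is already undefined.

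**Which rule governs.** The precedence note that closes Section 5.2.5.3 names only Sections 5.2.5.3.2.1 and 5.2.5.3.2.2, which concern avelumab. It does not rank the two M6620 rules.

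**Neighbouring events.** For Grade 4 neutropenia of 7 days or less, the first list states a 25% cut. The later text interrupts treatment for Grade 3 or higher M6620 toxicity and, if dosing is delayed and the patient may be benefiting, leaves a one-level cut to the investigator. For non-hematologic toxicity, the first list discontinues M6620 at Grade 3 and at Grade 4, while the later text reduces by one level at Grade 3 (with exceptions) and allows resumption two levels lower at Grade 4.

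**The case against.** The best reply is that the 50% is an inference. Section 5.2.5.3.1 does not define a dose level for de-escalation, and the only percentage it states is 25%, which appears again as the least further cut for a responding patient with toxicity after two reductions. If a level were a 25% step, both the size conflict and the missing dose would disappear. This stands as a reason to label the 50% as dependent on a reading. It does not remove the problem, because no section defines a level as a 25% step and the protocol uses the term for the Table 1 doses.

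A second reply is that the protocol has room to manoeuvre. The two-level step is permissive, the investigator may set the final reduction, exceptions go through the PI and the IND Office, and intermediate doses are possible after discussion with the drug supplier. Section 5.2.5.3 also accepts a dose or frequency reduction by agreement instead of stopping. All of this is correct, so it would go too far to infer that a patient at 240 mg/m² with a repeat event has no way to continue. But none of these provisions ranks the two rules or gives a value two levels below 240 mg/m².

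Four other inferences are tempting and not supported:
- That every Grade 4 hematologic event is in conflict. Only two listed events clearly overlap. Febrile neutropenia carries no grade, and shorter Grade 4 neutropenia is not in the second list.
- That first-cycle DLT evaluation is affected. The first list exempts Part A participants in the DLT observation period.
- That two 25% steps give 0.75² × 480 = 270 and 0.75² × 240 = 135 mg/m² for comparison. The first list says nothing about a second event or about compounding.
- That one paragraph is superseded and can be deleted. Nothing in the documents says so, and deleting the first list would silently settle the non-hematologic conflict too.

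**Conclusion.** Section 5.2.5.3.1 contradicts itself for Grade 4 thrombocytopenia and for Grade 4 neutropenia of more than 7 days, and nothing in the protocol resolves it. On the Table 1 reading, the two rules give resumption doses that differ by a factor of 1.5 after a first event: 360 against 240 mg/m² from 480, and 180 against 120 from 240. The repeat-event reduction has no defined dose for a patient who started at 240 mg/m², and a patient at 120 mg/m² has no lower level.

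Both figures rest on that reading of dose level. Without it, the two differently worded rules are still unranked, but the size of the gap is unknown. The conflict bears on safety after Cycle 1 and in expansion, and on how exposure behind the RP2D and the descriptive toxicity tables is read. It does not show that any DLT count or the MTD rule is wrong. This is an internal inconsistency in a dosing instruction for Grade 4 toxicity and needs to be reconciled.

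**What to change.** The sponsor and the Safety Monitoring Committee should reconcile the two rule sets in Section 5.2.5.3.1 and state:
- which one governs for each event covered by both;
- what a dose level means for de-escalation;
- whether a second reduction is counted from the original or the current dose;
- for each current dose (480, 240, 120 mg/m²) and each event number, the dose to resume at, or that no further level exists.

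A single table would hold this. Grade 4 neutropenia of 7 days or less should have its own entry. The non-hematologic conflict in the same section (discontinue, against reduce by one or two levels) should be settled in the same amendment. No paragraph should be deleted before those decisions are made. Which rule or dose is right is for the sponsor and the committee, and this point takes no view on it.

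The cost is a text change in the next amendment, with no extra patients, visits or procedures.

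### Section 5.2.5.3.1 both discontinues M6620 and allows its resumption after the same related Grade 3 or Grade 4 non-hematologic toxicity, and nothing says which rule governs

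*Combined protocol and SAP*

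**What the plan says.** All of the conflicting text is in Section 5.2.5.3.1, in this order:

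- **Opening sentence.** After an AE attributed to M6620, treatment may be interrupted, and the Investigator may resume it once toxicities are at Grade 2 or less.
- **Lead-in to items a–c.** M6620 may be reduced after a related AE, except for Part A participants in the DLT observation period. Exceptions to the criterion must be agreed between the PI and the IND Office.
- **Items b and c.** "For Grade 3 non-hematologic toxicity: M6620 will be discontinued" and "For Grade 4 non-hematologic toxicity: M6620 will be discontinued". Neither item exempts any type of toxicity.
- **Status of the guidelines that follow.** The Investigator may set the final reduction or delay. "However, these guidelines provide the minimum dose reduction or delay criteria".
- **Grade 3 or higher M6620 toxicity.** "treatment will be interrupted and may be resumed when all toxicities have returned to Grade 2 or lower, at the discretion of the Investigator". This rule applies "excluding fatigue or nausea/vomiting/diarrhea adequately managed by supportive care".
- **Grade 3 non-hematologic toxicity, if subsequently observed.** "the M6620 dose will be reduced by 1 dose level", the trigger being "Grade 3 non-hematologic toxicity (except for fatigue or nausea, vomiting, or diarrhea adequately controlled by medication". M6620 infusion, hypersensitivity and allergic reactions are referred to additional guidance.
- **Grade 4 non-hematologic toxicity.** "For Grade 4 non-hematologic toxicity, treatment will be interrupted and may be resumed with 2 dose level reductions", once it is back to Grade 2 or lower.

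Four other sections bear on the point. Section 5.2.5.2 calls for interruption or delay after potentially related Grade 3 or 4 toxicity, and holds Grade 3 or higher liver-test events until baseline or Grade 1 or lower. Section 5.2.5.3 halts and then restarts treatment after a DLT, and allows a reduction in place of discontinuation if the IND Office agrees. Sections 3.3 and 3.4 also foresee restarting or continuing after a DLT.

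**The concern.** This is the rule that sites will consult when deciding whether to give an investigational ATR inhibitor again, alongside avelumab, after a severe or life-threatening related event. Items b–c end M6620 unless two parties outside the bedside decision agree otherwise. The surrounding text leaves resumption to the Investigator and does not mention that agreement.

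An Investigator who resumes M6620 at Grade 2 complies with one part of the section and breaches another, unless an exception was agreed. Two patients with the same event may be handled in opposite ways, and a monitor could class the same re-dosing as compliant or as a deviation depending on the paragraph read. Safety and tolerability is a primary objective, and Section 3.3 lists many Grade 3 or higher non-hematologic events as DLTs, so the situation is foreseeable.

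**Working it through.** No figure in the plan depends on this text, so there is no arithmetic to reproduce. The check sets the two sets of instructions side by side for each class of related toxicity, and then looks for wording that decides between them.

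**Step 1: compare the actions.**

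| Related non-hematologic toxicity | Items b–c | Opening sentence and later guidelines of 5.2.5.3.1 |
|---|---|---|
| Grade 4 | Discontinue M6620 | Interrupt; may resume at Grade 2 or lower, two dose levels down |
| Grade 3, other than the next row | Discontinue M6620 | Interrupt; may resume at Grade 2 or lower at the Investigator's discretion; one dose level down if subsequently observed |
| Grade 3 fatigue, nausea, vomiting or diarrhea, adequately controlled | Discontinue M6620 | Exempt from both the interruption and the one-level reduction |

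The two columns differ in 3 of 3 rows. Two qualifications apply:

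- In the second row, infusion and hypersensitivity reactions go to separate guidance, so the one-level reduction does not simply apply to them. The conflict in that row does not rest on the reduction or on the word that limits it to later occurrences. The interrupt-and-resume rule already covers Grade 3 or higher without that limit.
- In the third row, Section 5.2.5.2 gives a third answer. It asks for interruption of potentially related Grade 3 toxicity and does not exempt controlled fatigue or gastrointestinal events. The protocol therefore gives three actions for one event: discontinue, interrupt, or neither interrupt nor reduce.

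**Step 2: look for text that ranks the two sets.**

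- *Exception clause in the lead-in.* It shows how to depart from the criterion. It does not say whether resuming under the later guidelines counts as a departure.
- *Minimum-criteria sentence.* It lets the Investigator be stricter. Stopping M6620 thus satisfies both sets, while resuming satisfies only the later one. It does not say whether resuming is allowed.
- *Part A clause.* As worded it limits dose reductions during the DLT observation period. It does not allot the two sets to different phases.
- *Reduction in place of discontinuation (Section 5.2.5.3).* It follows text on recurrent and intolerable toxicity, so its reach here is arguable. It requires IND Office agreement, which the resumption rules in 5.2.5.3.1 do not mention.
- *Precedence note closing the general text of Section 5.2.5.3.* It names only the two avelumab subsections, 5.2.5.3.2.1 and 5.2.5.3.2.2.
- *Sections 3.3, 3.4, 5.2.5.2 and 5.2.5.3.* All four lean toward interrupting and restarting, which makes items b–c look like the outlier. None overrides them, and Section 3.3 sends the reader back to Section 5.2.5, where the conflict sits.

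No sentence was found that ranks one set above the other.

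**The case against.** The strongest reply is that the section can be read coherently and conservatively: stop M6620 by default, and use the later reductions when the PI and the IND Office agree. IND Office agreement is named both in the lead-in and in Section 5.2.5.3, and all the resumption wording is permissive. That reading is sensible, and the fix below adopts it, but the protocol does not state it. The later guidelines give the decision to the Investigator without mentioning agreement.

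A second reply is that discontinuation in items b–c need not be permanent. The protocol usually adds that word for avelumab, and Table 2 speaks of temporarily discontinuing an infusion. This cannot be excluded, but Section 5.2.5.3.1 uses interruption for a hold, and items b–c are its only discontinuation instructions under a heading that announces them. Even read as a hold, they would still conflict with the exemption for controlled Grade 3 fatigue and gastrointestinal events.

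A third reply is that the Part A clause may govern the whole list, so that items b–c do not bind Part A during the DLT observation period. If so, the conflict is absent there but remains at all other times.

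Two stronger readings are tempting. A reader might infer that the protocol requires re-dosing after a life-threatening event. It does not: every resumption rule is optional, and stopping always complies. A reader might also infer that controlled Grade 3 fatigue or gastrointestinal events need no action under the protocol as a whole. That holds only within the later guidelines of 5.2.5.3.1, because Section 5.2.5.2 still asks for interruption.

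**Conclusion.** The contradiction stands on the face of Section 5.2.5.3.1. It affects all three classes of related Grade 3–4 non-hematologic toxicity that the section separates, and no wording says which set governs or whether PI and IND Office agreement is needed before resuming. The conclusion assumes that discontinuation in items b–c means ending M6620, as the section's separate use of interruption indicates.

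The consequence is limited to patient handling and the judgement of protocol compliance. A reader might infer that dose escalation decisions or the toxicity stopping rule are affected. The documents do not support that: Section 3.3 classifies the toxicity, not the later choice between stopping and resuming, and no DLT count or stated statistical figure changes. It should still be corrected, because a re-dosing safety rule ought to give one answer for one event and a text change is enough.

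**What to change.** Amend Section 5.2.5.3.1 to a single table with one action per toxicity class and grade.

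- **Recommended default.** Discontinue M6620 for related Grade 3 or Grade 4 non-hematologic toxicity. Allow resumption at the reduced doses already given in the section only on documented PI and IND Office agreement. This fits the existing exception clause and the IND Office agreement step in Section 5.2.5.3. Bring the opening sentence into line, and add an explicit row for controlled Grade 3 fatigue, nausea, vomiting and diarrhea that agrees with Section 5.2.5.2.
- **If routine resumption is intended.** Delete items b–c and align the recovery threshold with Section 5.2.5.2. That section holds Grade 3 or higher liver-test events until baseline or Grade 1 or lower, while 5.2.5.3.1 resumes at Grade 2, so deletion alone would leave a mismatch.
- **Secondary clarification.** The section uses both percentage cuts (25%) and dose-level cuts. State whether a dose level means a step on the 480/240/120 mg/m² ladder or a percentage, and say that M6620 stops when no lower permitted dose exists.

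The cost is one protocol amendment, after the sponsor and the Safety Monitoring Committee decide on rechallenge. Sample size, visits and statistical design do not change. Under the default, some patients who are benefiting from M6620 would need an agreement step before resuming.
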